#### **4.4.1. Trial Stopping Rules**

If any of the following occur, administration of the IMP will be stopped, and recruitment will be put on hold at least temporarily until DMC feedback is received to confirm if the trial can continue:

1. AEs or frequency of AEs that, in the judgment of the sponsor, are deemed to warrant immediate review by the DMC
2. Any other safety finding assessed as related to Lu-DTPA-omburtamab that, in the opinion of the DMC or sponsor, contraindicates further dosing of trial patients.

If any of these occur, an immediate cumulative review of safety data with focus on the AE in question will be conducted by the DMC to determine whether dosing and further recruitment should be resumed, the protocol modified, or whether the trial should be discontinued. Review and approval of the Sponsor Safety Committee and approval by the regulatory authorities is

required for resumption of the trial, should the trial be interrupted due to one of the above-mentioned safety findings.

Any patients who have received the IMP and are currently in the trial at the time trial stopping criteria are met will continue to be followed by the investigator for safety.

#### 4.5. Trial Termination

The sponsor reserves the right to close a trial site or terminate the trial at any time for any reason at the sole discretion of the sponsor. Trial sites will be closed upon trial completion. A trial site is considered closed when all required documents and trial supplies have been collected and a trial site closure visit has been performed. Reasons for trial termination may include, but are not limited to:

- Related AEs not previously reported with any similar investigational trial treatment with respect to their nature, severity, and/or duration
- Increased frequency and/or severity and/or duration of known, anticipated, or previously reported AEs or pre-existing conditions
- Medical or ethical reasons affecting the continued performance of the trial
- Difficulties in the recruitment of patients
- Cancellation of drug development.

The investigator may initiate trial site closure at any time, provided there is reasonable cause and sufficient notice is given in advance of the intended termination. Reasons for the early closure of a trial site by the sponsor or investigator may include, but are not limited to:

- Failure of the investigator to comply with the protocol, the requirements of the IRB/EC or local regulatory authorities, the sponsor's procedures, or Good Clinical Practice (GCP) guidelines
- Inadequate recruitment of participants by the investigator.

## 5. TRIAL TREATMENTS

### 5.1. Treatments Administered

Omburtamab is a murine IgG1 monoclonal antibody that recognizes tumor-associated antigen B7-H3. DTPA-omburtamab will be radiolabeled with lutetium-177 at a dedicated GMP facility. Lu-DTPA-omburtamab is a clear, colorless to slightly yellow, and particle free solution.

Lu-DTPA-omburtamab will be administered via an indwelling intracerebroventricular access device (e.g., Ommaya catheter). The infusion reservoir must be flushed with human serum albumin (HSA) and autologous CSF after each infusion. For detailed instructions, please refer to the IMP manual. For all infusions, emergency support for anaphylaxis must be readily available, including epinephrine, diphenhydramine, hydrocortisone, and/or dexamethasone at the bedside.

In Part 1 Cycle 1, the dosimetry and treatment doses should be administered under controlled conditions with inpatient care for at least 24 hours after IMP administration. As a routine precaution, patients must be monitored during the infusion and with close observation for two hours after the infusion with readily available resuscitation equipment and access to emergency units. Staff should be qualified in resuscitation and the physician must be readily accessible for assistance during the day of the infusion. The infusion reservoir must be flushed with human serum albumin and CSF after each infusion. The patient must be observed regularly, and the patient can be discharged after 24 hours if no safety issues are observed.

In Part 1 Cycle 2 and in Part 2, patients can be treated in an outpatient setting or can be admitted as inpatients for infusions; however, all patients should be observed for a minimum of 2 hours after the end of infusion and can be released if no safety issues are observed.

For radiation safety, see [Section 5.2.2](#).

In Part 1 only, for the first 5-week treatment cycle, a 5 mCi dosimetry dose will be administered on Day 1 and a treatment dose will be administered on Day 8. However, if a patient experiences a Grade 3 or 4 non-hematologic AE or other DLT after receiving the dosimetry dose, the treatment dose will not be administered, and the patient will be discontinued from trial treatment. If the dosimetry dose of 5 mCi turns out to deliver a too low acquisition of radioactivity count (see [Section 7.2](#)), the dosimetry dose may be increased to 10 mCi for subsequent patients, at the sponsor's discretion. In the second treatment cycle of Part 1 (if applicable) and throughout Part 2, a treatment cycle will consist of a treatment dose on the first day of each cycle. Patients who are not discontinued from treatment will be eligible for treatment at the same dose administered in the first cycle, up to a maximum of 2 cycles in Part 1 and 5 cycles in Part 2.

### 5.2. Preparation, Storage, Handling, and Accountability

Only patients enrolled in the trial may receive trial treatment and only authorized site staff may supply or administer trial treatment. The investigator, institution, or the head of the medical institution (where applicable) is responsible for trial treatment accountability, reconciliation, and record maintenance (i.e., receipt, reconciliation, and final disposition records). There is no long-term storage of IMP at site, and the IMP will be prepared on demand when a patient is

found to be eligible for the trial and when further cycles (if applicable) are scheduled. The utensils used to ship, prepare, and administer the IMP will be radioactive and should be destroyed according to local regulations. The destruction can be performed without sponsor approval but only after accountability (see [Section 5.5](#)) has been conducted.

Doses must be aseptically prepared at a designated radiopharmacy by withdrawal of Lu-DTPA-omburtamab from the single-use vial into a sterile syringe to the target activity confirmed by dose calibration. The finished product in liquid form is drawn into a syringe and then placed in a lead container (“pig”) that is then placed inside a lead-lined container and transported to the patient’s bedside prior to administration. For detailed instructions, please refer to the IMP manual.

At each clinical site, the actual Lu-DTPA-omburtamab dose administered should be assayed immediately prior to administration to verify that the prescribed activity and the activity actually administered agree within  $\pm 10\%$  (see [Table 3](#)). The amount of radioactivity infused in patients should be assessed by measuring radioactivity of the infusion syringe before and after Lu-DTPA-omburtamab infusion into the indwelling intracerebroventricular access device (e.g., Ommaya catheter) and subtracting the post infusion count from the pre infusion count. The radiolabeled Lu-DTPA-omburtamab is administered via a catheter with an inline filter.

**Table 3: Accepted Activity Ranges for Dosimetry and Treatment Doses**

	Nominal Dose (Acceptable Range) of Lutetium-177
Dosimetry Dose (Day 1, Cycle 1, prior to all treatment dose levels in Part 1)	5 (4.5 – 5.5) mCi
Dose Level 1 Treatment Dose	10 (9.0 – 11.0) mCi
Dose Level 2 Treatment Dose	25 (22.5 – 27.5) mCi
Dose Level 3 Treatment Dose	50 (45.0 – 55.0) mCi
Dose Level 4 Treatment Dose	65 (58.5 – 71.5) mCi
Dose Level 5 Treatment Dose	85 (76.5 – 93.5) mCi

The investigator or designee must confirm appropriate temperature conditions have been maintained during transit to the radiopharmacy. Temperature-controlled shipment from radiopharmacy to the clinical department is not required.

All trial treatments must be stored in a secure, environmentally controlled, and monitored (manual or automated) area in accordance with the labeled storage conditions with access limited to the investigator and authorized site staff.

Further guidance and information for the final disposition of unused trial treatment will be provided in the IMP manual.

### 5.2.1. Radiolabeling of DTPA-omburtamab

Lu-DTPA-omburtamab is manufactured by conjugating the monoclonal antibody omburtamab with p-SCN-Bn-CHX-A''-DTPA followed by radiolabeling of the conjugate DTPA-omburtamab (DTPA-omburtamab drug product intermediate) with lutetium-177 to create the final Lu-DTPA-omburtamab drug product.

The conjugation of omburtamab is performed by a conjugation of p-SCN-Bn-CHX-A''-DTPA ([(R)-2-Amino-3-(4-isothiocyanatophenyl)propyl]-trans-(S,S)-cyclohexane-1,2-diamine-pentaacetic acid) to lysine side chains of the monoclonal antibody in a chelator-to-antibody ratio (CAR) of 3.

The DTPA-omburtamab drug product intermediate is then radiolabeled with the  $\beta$ -emitter lutetium-177, and shipped to the radio pharmacy affiliated with the clinical trial site.

The required activity should be withdrawn into a syringe using aseptic technique using a dose calibrator and the rest of the activity should be discarded in accordance with local regulations. Radiolabeled product is sterilized by filtration. Quality control is ensured according to a release specification, also including endotoxin testing, bioburden, and radioimmunoassay.

### 5.2.2. Radiation Safety

Local safety instructions for storage and handling of radioactive drug products must be strictly followed. Radiation safety precautions may include patient isolation and the use of lead shielding, or designated rooms to ensure that the dose rate in the surrounding areas meets regulatory requirements.

For treatment in Part 1 Cycle 1, see [Section 5.1](#). In Part 1 Cycle 2 and in Part 2, patients can be treated in an outpatient setting or can be admitted for Lu-DTPA-omburtamab administration; however, all patients should be observed for a minimum of 2 hours after end of each infusion. When patients are admitted, the caregiving staff will be instructed in radiation safety steps required to minimize exposure to themselves according to local guidelines.

The dose rate from the patient will be measured after end of infusion and at later timepoints to define the need for overnight stay(s) using portable radiation detectors as described in the local safety instructions. Patient release timepoint following administration of a dose of Lu-DTPA-omburtamab will be determined based on the dose rate criterion specified in § 35.75 in [NUREG 1556, Volume 9, Rev 3](#) and [Regulatory Guide 8.39, Rev 1](#) (US sites) or based on local radiation safety requirements (sites outside US). Patients can be released following administration of dosimetry or treatment doses of Lu-DTPA-omburtamab if the total effective dose equivalent to any other individual from exposure to the released individual is not likely to exceed 5 mSv (~ 500 mrem) or the value described by local safety instructions, whichever is the lowest. Patient isolation will remain in effect until the dose rate is below what is required in accordance with local patient release regulations.

The site's radiation safety service will manage the collection, shielding, and waste disposal, as appropriate, for patient excreta for each case. Following release of the patient, the site's radiation safety service will survey and perform decontamination procedures in the room to ensure that the room meets regulatory requirements.

Patients and legal guardians will be given instructions by radiation safety staff on how to handle waste and steps and procedures to follow to minimize radiation exposure to themselves, household contacts, the general public, and possible patient family caregiver(s), including pregnant women, and small children. Safety precautions will be taken to ensure that doses to

these caregivers are maintained as less than local safety instructions (e.g., 5 mSv [ $\sim$  500 mrem]). Patients and/or caregivers will be provided with a written instruction detailing radiation safety precautions as per the local requirements. The caregiver will agree to radiation safety instructions prior to administration of the IMP.

Safety instructions must include the following general precautions: Close contact (less than 1 meter) with other people should be limited for 7 days following an administration of Lu-DTPA-omburtamab. For other children and/or pregnant women, close contact (less than 1 meter) should be limited to less than 15 minutes per day for 7 days. Patients should sleep more than 1 meter from other people for 7 days and in a separate bedroom from other children and/or pregnant women for 15 days following an administration of Lu-DTPA-omburtamab.

### **5.2.3. Ventriculo-peritoneal Shunts**

Ventriculo-peritoneal shunts with programmable valves are allowed; however, the VP shunt must be closed (or adjusted to highest pressure setting) during IMP infusion and up to approximately 5 hours after IMP administration and then re-adjusted. The shunt re-adjustment times are at the discretion of the treating physician. Closure of the VP shunt is done at the discretion of the treating physician and the VP shunt should at any time based on patient safety evaluation be re-opened at the assessment of the treating physician.

## **5.3. Method of Treatment Assignment**

This is an open-label trial and is not subject to randomization. After dose level 1 in Part 1, patients will be allocated to the highest dose level cleared by the DMC.

### **5.3.1. Dose Modification**

Dose reductions will not be allowed in Part 1. If a dose reduction is needed in Part 1, the patient should be discontinued from treatment and all EOT Visit assessments completed.

In Part 2, dose reductions in individual patients are permitted where warranted due to toxicity. If dose reduction is needed in Part 2, the reduced dose will be decided upon agreement between the treating investigator and sponsor, guided by the safety and calculated absorbed doses to CSF and blood findings from Part 1.

For patients in Part 1 or 2 presenting with ongoing Grade 3 or 4 myelosuppression in the fifth week of a treatment cycle, and who are otherwise eligible for an additional treatment cycle, a delay of dosing in the next cycle for up to 8 weeks can be introduced, provided that the myelosuppression has sufficiently declined to Grade  $\leq 2$ . Dose delay will be enforced at the discretion of the treating investigator.

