###### ***4.3.2.1. Discontinuation of Trial Treatment***

Patients may withdraw from the trial treatment at any time at his/her own request or may be discontinued from trial treatment at any time at the discretion of the investigator for safety, behavioral, or administrative reasons. If the patient withdraws consent for disclosure of future information, the sponsor may retain and continue to use any data collected before such a withdrawal of consent. Additionally, patients may request destruction of any samples taken and not tested, and the investigator must document this in the site trial records. Refer to the Schedule of Assessments ([Appendix 3](#)) for data to be collected at the time of treatment discontinuation (EOT visit) and follow-up and for any further evaluations that need to be completed.

The patient must be permanently discontinued from treatment if any of the following occur:

- After receiving the dosimetry dose only, Grade 3 or 4 non-hematologic AE (including an AE considered to be a Grade 3 or 4 nervous system disorder; see [Section 7.1.5](#))
- DLT occurring before the end of Cycle 1 in each dose level in Part 1
- Grade 4 infusion-related reaction/anaphylaxis, or Grade 3 infusion-related reactions (excluding fever and Grade 3 abnormal laboratory values) that do not resolve to Grade  $\leq$  1 within 5 days of onset

- Grade 4 neurological AE
- Development of obstructive or symptomatic communicating hydrocephalus
- Grade 4 treatment-related AEs (excluding infusion-related fever, and non-life-threatening laboratory values)
- Disease progression before Cycle 2 in Part 1 or Cycle 5 in Part 2
- Any medical or safety reason, in the opinion of the investigator or sponsor
- Chemical meningitis (symptoms of clinical meningitis but cultures for infectious agents were negative) in which either: a) event is non-responsive to IV steroids, b) radiologic or operative intervention was indicated, or c) focal neurologic deficit was present
- The patient receives prohibited therapy and/or undergoes procedures during the trial that, in the opinion of the investigator, warrant treatment discontinuation
- Patient decision
- Pregnancy.

A patient who is discontinued from treatment, but for whom consent is not withdrawn, shall continue to be followed for the entire trial period.

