### 7.3.2. Response Evaluation, Overall Response Rate, and Duration of Response

Response, as defined by the RAPNO criteria (Warren et al. 2018; see Appendix 6) will be assessed in Part 1 at the EOT Visit. In Part 2, response will be assessed at end of Cycle 1 and Cycle 3, EOT Visit, then 26, 39, and 52 weeks post first dose, followed by 78 and 104 weeks post first dose of Lu-DTPA-omburtamab. Notably, objective response and stable disease requires that all criteria are met, while progression is defined when any of the PD criteria are met.

The ORR will be calculated from baseline MRI scans and from scans after the dosing of Lu-DTPA-omburtamab using 2 methods: firstly, by considering MRI data, neurological examination, and CSF cytology data together (RAPNO criteria); secondly, by considering CSF cytology data only. ORR will be defined as the proportion of all evaluable patients achieving a CR or PR as best overall response at the time of assessment.

Investigator-assessed DoR (Part 2) is defined as the time from response (CR or PR) to progression. Patients without any sign of progression will be censored at the date of their last PFS assessment.

In Part 1 and Part 2, the baseline CSF cytology assessment must be completed within 3 weeks prior to the first Lu-DTPA-omburtamab treatment dose infusion. Cerebrospinal fluid cytology should be assessed as positive/negative. Cerebrospinal fluid cytology will be assessed in Part 1 at screening, the EOT Visit, and in Part 2 at screening, end of Cycle 1 and Cycle 3, EOT Visit, and at each Follow-up Visit.

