 The Lu-DTPA-omburtamab Treatment Period is divided into 5-week cycles. In Part 2, a cycle consists of a treatment dose on Day 1. The patient can receive up to 5 cycles at the discretion of the investigator. The infusion reservoir must be flushed with HSA and CSF after each infusion. The patient will be observed post treatment to decide if further cycles can be administered.

Day 1, 15, and 29 for Cycles 2 to 5 correspond to Day 36, 50, and 64 (for Cycle 2), Day 71, 85, 99 (for Cycle 3), 106, 120, 134 (for Cycle 4), and 141, 155, and 169 (for Cycle 5). Adjustments to the dosing schedule will be accommodated on a patient-by-patient basis depending on the clinical condition of the patient.

 If the IMP is discontinued prior to completion of all scheduled visits of the cycle (i.e., up to and including Day 29), the treatment visits that fall after the date of the EOT Visit should be skipped, and the patient should move directly into the follow-up phase. If the IMP is discontinued after Cycle 1, an unscheduled visit (including MRI etc.) should be done at 13 weeks post first dose.

 All patients who are dosed with Lu-DTPA-omburtamab in Part 2 should be followed up regularly (every 13 [±2] weeks, i.e., 26, 39, and 52 weeks post first dose, then every 26 [±2] weeks, i.e., 78 and 104 weeks post first dose, and thereafter annually) for monitoring of secondary malignancies during the trial and for at least 10 years after the end of trial, or until death, if sooner.

 Informed consent must be obtained before any trial-related procedures. If the indwelling ICV access device (e.g., Ommaya) is placed in connection with the tumor resection, the informed consent must be obtained prior to the surgery, and before the start of the screening period, unless this is placed as part of a standard of care procedure at site. If any procedures/tests are from before informed consent is obtained, it must be clear from source documents that this was not performed for the purpose of the present trial. In these cases, the procedures/tests do not need to be repeated at the Screening Visit if they were performed within the allowed timelines. The investigator is responsible for documenting this properly.

 Only anti-cancer therapy.

 Physical examinations to be performed at screening and as clinically indicated.

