 Measurements of heart rate, respiratory rate, temperature, and blood pressure. On dosing days, measurements to be taken before and 30 min after the end of the IMP infusion.

 Lansky Scale <16 years, Karnofsky Scale ≥16 years.

 To be performed within 3 weeks prior to first IMP infusion. May be performed on the first dosing day but it must be before IMP administration.

 MRI of the brain and spine will be completed before first IMP administration and at the End-of-Cycle (Day 29) Visit for Cycles 1 and 3 only (±4 days of the actual visit date), EOT Visit (preferably ±4 days of the actual visit date), and each Follow-up Visit (±2 weeks of the actual visit date). MRI can be performed on a different day to the other visit assessments, in accordance with investigational site standards.

 Will be used to evaluate safety and efficacy.

 Beginning 24 hours before Lu-DTPA-omburtamab administration, divided into twice-daily doses for a total of 3 days.

 Given 1-2 hours prior to Lu-DTPA-omburtamab administration, including oral acetaminophen/paracetamol and antihistamine (e.g., diphenhydramine).

 In accordance with [Appendix 1](#) and until the first follow-up visit.

 If CSF cytology sample is positive, it must be repeated within 4 weeks of the positive sampling.

 Cycles 1 and 3 only.

 Drawn and held for culture only if elevated body temperature after dosing suggests infection rather than expected response to ICV dosing. Samples to be taken within 6 hours after completion of Lu-DTPA-omburtamab infusion.

 The ADA samples must be drawn prior to dosing. Serum and CSF samples for ADA analyses will be drawn at baseline, at the start of Cycle 2 (predose), and after last treatment. Presence of ADA will be analyzed at a central laboratory.

 Blood and CSF samples for pharmacokinetics will be drawn in Cycles 1 and 2 only, as per [Table 5](#).

 Pregnancy testing (serum or urine) is mandatory for women of childbearing potential at screening, prior to each dose, and at the EOT Visit.

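### In Part 2 the second on-treatment MRI and CSF cytology follow cycle number, so dose delays for marrow toxicity widen the gap after the day 29 scan from 70 to 126 or 154 days

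*Combined protocol and SAP*

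**What the plan says.** **Delay.** Section 5.3.1 covers patients "presenting with ongoing Grade 3 or 4 myelosuppression in the fifth week of a treatment cycle" who could otherwise go on to another cycle. For them "a delay of dosing in the next cycle for up to 8 weeks can be introduced", once the myelosuppression has eased. No limit is set on how many cycles may be delayed. Table 8, footnote 1 adds: "Adjustments to the dosing schedule will be accommodated on a patient-by-patient basis depending on the clinical condition of the patient".

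**Assessments.** Footnote 10 of Table 8 places the on-treatment MRI "at the End-of-Cycle (Day 29) Visit for Cycles 1 and 3 only", and footnote 16 does the same for CSF cytology. Section 7.3.2 gives the whole sequence: "response will be assessed at end of Cycle 1 and Cycle 3, EOT Visit, then 26, 39, and 52 weeks post first dose", then weeks 78 and 104.

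**Catch-up scan.** Under footnote 2, if treatment stops after Cycle 1, "an unscheduled visit (including MRI etc.) should be done at 13 weeks post first dose". Nothing equivalent is given for a patient who is delayed but still on treatment.

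**Later visits.** Footnote 3 applies weeks 26, 39, 52, 78 and 104, counted from first dose, to all patients dosed in Part 2. The table, however, puts them under Follow-up, after the end-of-treatment (EOT) column, and Section 3.1.3 counts follow-up to 104 weeks after the last infusion.

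**Use.** Section 8.4.1 plans Kaplan-Meier estimates of median PFS, 1- and 2-year PFS and median DoR, together with ORR. Section 4.3.2.1 lists among the reasons to stop treatment: "Disease progression before Cycle 2 in Part 1 or Cycle 5 in Part 2".

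**The concern.** Progression or response that shows only on MRI or cytology is normally dated at the assessment that finds it. Backdating is provided only for neurological deterioration (Appendix 6, note a). If the second assessment moves with Cycle 3, its date depends on how much marrow toxicity the patient had. Median PFS and DoR then partly reflect the delay pattern, and time of response is affected in the same way. The plan recognises the early gap for patients who stop after Cycle 1 and fills it with a week 13 scan, but leaves it open for delayed patients who may be dosed again. In those patients the most recent MRI is also older at the next dose, although progression is a reason to stop.

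**Working it through.** **1. The plan's own calendar.** Day 29 of cycle k falls on day 1 + 35(k − 1) + 28. Cycle 1 gives day 29 and Cycle 3 gives day 99, as in Table 8, footnote 1. The planned gap is 99 − 29 = 70 days.

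**2. Adding 8-week (56-day) delays before Cycle 2 or 3.** Cycle 3 Day 29 moves to day 155 with one delay and day 211 with two. Week 26 is day 183. The gap is 155 − 29 = 126 days with one delay. With two it is 183 − 29 = 154 days if week 26 is kept on treatment, or 211 − 29 = 182 days if not. The fifth dose is nominally on day 141 (week 20). Taking EOT at 5.5 weeks after the last dose (5 to 6 allowed), EOT falls at week 25.5 plus 8 per delay. With the calendar visits kept:

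| Delays | Scan weeks to week 52 | Gap after week 4 | Scans by week 26 / 52 |
|---|---|---|---|
| none | 4, 14, 25.5, 26, 39, 52 | 10 weeks | 4 / 6 |
| one | 4, 22, 26, 33.5, 39, 52 | 18 weeks | 3 / 6 |
| two | 4, 26, 30, 39, 41.5, 52 | 22 weeks | 2 / 6 |
| four | 4, 26, 30, 39, 52 | 22 weeks | 2 / 5 |

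If weeks 26 to 52 are done only after EOT, two delays leave weeks 4, 30, 41.5 and 52, and four delays leave 4, 30 and 57.5.

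**3. Detection lag within the gap.** Assume exponential PFS with median m (13 to 26 weeks; not in the documents) and progression found only by scan. With λ = ln 2/m, the mean lag in a gap G is G/(1 − e^(−λG)) − 1/λ. For G = 126 days and m = 91 days this is 126/0.617 − 131.3 = about 73 days. Over m = 13 to 26 weeks:

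- 70-day gap: 37–38 days
- 126-day gap: 68–73 days
- 154-day gap: 84–92 days
- 182-day gap: 101–111 days

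**4. Effect on the planned estimates, calendar visits kept.** If all progressions are found by scan, the observed curve at week t averages S(last scan) over patients, with S(t) = 0.5^(t/m).

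- m = 13, no delay: S(14) = 0.474, so the observed median is 14 weeks.
- m = 13, 25% delayed once: week 14 gives 0.75 × 0.474 + 0.25 × 0.808 = 0.558; week 22 gives 0.75 × 0.474 + 0.25 × 0.309 = 0.433. Median 22.
- m = 13, 25% delayed twice: the curve first falls below one half at week 25.5 (0.75 × 0.257 + 0.25 × 0.808 = 0.395). Median 25.5.
- m = 17, no delay: S(14) = 0.565 and S(25.5) = 0.354. Median 25.5.
- m = 17, 50% delayed once: week 22 gives 0.5 × 0.565 + 0.5 × 0.408 = 0.486. Median 22, which is lower.
- m = 39: the median is 39 throughout, since everyone is scanned at week 39.
- Weeks 52 and 104: everyone is scanned, so the estimates are S(52) and S(104) whatever the delays (25.0% at 1 year for m = 26).

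A simulation of 400,000 patients per scenario agrees. In it, mean PFS restricted to 52 weeks rises by 0.1 to 0.9 weeks with 25% delayed and by at most 3.5 weeks if all are delayed twice. If half of progressions are found clinically at onset, the m = 13 median moves from 14 to 15.2 weeks with 25% delayed.

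**5. Age of the last MRI at the next dose.** An 8-week delay before Cycle 2 puts that dose on day 36 + 56 = 92 and the Cycle 3 dose on day 71 + 56 = 127. The day 29 MRI is then 63 and 98 days old, against 7 and 42 as planned.

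**6. With the scan at week 13 or 14.** Weeks 4, 13 or 14, 26, 39 and 52 give a longest gap of 13 weeks to week 52, whatever the delay.

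**The case against.** A reader might infer that children with marrow toxicity are scanned less often overall and that PFS is overstated. The documents do not support either statement. The visits from week 26 are counted from first dose, and footnote 3 applies them to every dosed patient. On that reading one or two delays leave six scans by week 52, as planned; what changes is the spacing before week 26. The 1- and 2-year proportions do not move, and the median can rise, fall or stay put.

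Imaging is also not the only route to progression. Neurological examination is scheduled on Day 1 and Day 29 of every cycle, and unexplained clinical worsening counts as progression. This limits the effect but does not remove it. The examinations are themselves tied to cycles, so in an 8-week delay none is scheduled for the 63 days from Day 29 to the next Day 1. They also cannot show progression without symptoms.

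The frequency of delay is unknown. Section 1.2.1 gives cytopenia in 81.7% and 87.5% of patients on the iodine-131 product, but without grade; those figures are not rates of qualifying delay. Section 1.1 expects that the lutetium label may reduce myelosuppression.

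A reader might also infer that a week 14 scan would prevent dosing after unseen progression. It would not do so in general: day 99 falls after a Cycle 2 dose delayed to day 92, when the MRI would still be 63 days old. Only the later figure improves, from 98 days to 127 − 99 = 28 days at the Cycle 3 dose.

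Finally, Part 2 is single-arm with about 24 patients and PFS is secondary, so no between-arm comparison is biased. That limits the weight of the point.

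**Conclusion.** The point holds as one about timing. The interval after the day 29 scan depends on toxicity: 70 days as planned, 126 with one maximal delay, and 154 or 182 with two, according to whether week 26 is kept on treatment. Reference to first dose and to all dosed patients favours keeping it, but the placement after EOT leaves this unsettled. The day counts follow from the protocol alone.

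The consequence is distorted timing of scan-detected progression, response and DoR, and a median PFS that can shift either way. Its size rests on assumed values for the true median, the share delayed and the share detected clinically. The upward shift is clearest if true median PFS is about three months. One- and 2-year PFS are unaffected if the calendar visits are kept for everyone. Under the post-EOT reading the 1-year estimate is also exposed: with four maximal delays no scan falls between weeks 30 and 57.5. Visit windows and missed scans were not modelled.

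**What to change.** In Table 8, footnotes 10 and 16, and in Section 7.3.2, state two things:

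- For patients still on treatment whose Cycle 3 Day 29 is postponed, the end-of-Cycle-3 MRI and CSF cytology are done at about week 13 to 14 from first dose instead, in line with the week 13 visit already in footnote 2.
- The week 26, 39, 52, 78 and 104 assessments apply on schedule to patients still on treatment.

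Keep the neurological examinations at cycle visits, the schedule for undelayed patients, and the current schedule for patients who have stopped. The week 13 to 14 assessment is then moved and not added, which matters given possible sedation for MRI and the limit on CSF volume.

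The cost is wording in two footnotes and one section. In delayed patients this scan no longer coincides with an end-of-cycle visit and may follow fewer doses: with one 8-week delay before Cycle 2, day 99 follows two doses (days 1 and 92) instead of three. Sites that had read the week 26 to 52 visits as post-EOT only would do more scans in delayed patients than they had expected. The change concerns assessment timing only and sets no dosing rule.
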